4.1.2. Part 2 Inclusion Criteria

1. Histological or cytological diagnosis of locally advanced or metastatic NSCLC (squamous or non-squamous histology) meeting the following criteria:
 - a. Receipt of at least 1, but not more than 2, prior treatment regimens in the advanced disease setting. In addition to participants with established metastatic or recurrent disease, the advanced disease setting also includes participants with platinum-based adjuvant, neoadjuvant, or definitive chemoradiation therapy given for locally advanced disease followed by recurrent or metastatic disease within 6 months of completing therapy.

- b. Prior treatment must have included an anti-PD-1/PD-L1 and a platinum-based chemotherapy, which may have been given in combination, or sequentially;
 - c. Prior treatment must have included an appropriate TKI if activating mutations are present, eg, EGFR/ALK/ROS1/BRAF/RET/TRK;
 - d. Most recent treatment must have included anti-PD-1/PD-L1 for at least 4 months, without radiographic disease progression, followed by confirmed radiographic disease progression on or within 12 weeks of the last dose;
 - e. No more than 1 prior anti-PD-1/PD-L1 treatment regimen may have been given;
 - f. Prior anti-PD-1/PD-L1 may not have been discontinued permanently for toxicity.
 - g. No prior treatment may have been given with any immunologic therapy other than anti PD-1 or PD-L1.
2. A mandatory archived formalinfixed paraffin embedded (FFPE) tumor tissue block (preferred) must be provided. If an FFPE tumor tissue block cannot be provided, sites should contact sponsor for approval to submit slides. If an archived FFPE tissue is not available, a de novo (ie, fresh) tumor sample can substitute and should be obtained in accordance with local institutional practice for tumor biopsies.
3. Females and/or male participants age ≥ 18 years.
4. Eastern Cooperative Oncology Group (ECOG) Performance Status (PS) 0 or 1.
5. Measurable disease as per RECIST v. 1.1.
6. Adequate Bone Marrow Function, including:
 - a. Absolute Neutrophil Count (ANC) $\geq 1,500/\text{mm}^3$ or $\geq 1.5 \times 10^9/\text{L}$;
 - b. Platelets $\geq 100,000/\text{mm}^3$ or $\geq 100 \times 10^9/\text{L}$;
 - c. Hemoglobin $\geq 9 \text{ g/dL}$.
7. Adequate Renal Function, including:

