7.4. Tumor Response Assessments

Tumor assessments will include all known or suspected sites of disease. Screening images may be obtained within 5 weeks of registration. Imaging obtained as part of standard of care that are performed within 28 days (-7 days) of registration may be used for screening assessment. Imaging will include (a) CT scan (computerized tomography) of the chest, abdomen and pelvis, or magnetic resonance imaging (MRI) of these same areas, and (b) bone scan, for participants with known or suspected bone metastases. Baseline brain imaging (CT or MRI) is not required, except in the case of symptomatic participants to rule out brain metastases (see Section 4).

The same imaging technique (CT scan or MRI) used to characterize lesions identified at baseline should be employed when performing on-study tumor assessments. As the intention of administration of VBIR-2 is to activate an anti-tumor immune response in the vaccine draining lymph nodes, the inguinal (limb) and axillary (arm) lymph nodes should not be used as target lesions, since injections of antigens may be given in the upper arm or thigh. It is possible that lymph nodes draining the upper arm or thigh may become enlarged following administration of the VBIR-2, and may not accurately reflect the status of underlying disease.

Anti-tumor activity will be assessed through radiological tumor assessments conducted at baseline; during treatment as specified in the [SOA](#); whenever disease progression is suspected (eg, symptomatic deterioration); and at the time of withdrawal from treatment (if not done in the previous 6 weeks).

Assessment of response will be made using RECIST version 1.1 ([Appendix 3](#)).

All participants' files and radiologic images must be available for source verification and for potential peer review. In addition, historical images (collected up to one year prior to study entry) may be requested for potential peer review.

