All sites of disease must be assessed at baseline. Baseline assessments should be done as close as possible prior to study start. For an adequate baseline assessment, all required scans must be done within 28 days prior to treatment and all disease must be documented appropriately. If baseline assessment is inadequate, subsequent statuses generally should be indeterminate.

Target lesions

All measurable lesions up to a maximum of 2 lesions per organ, 5 lesions in total, representative of all involved organs, should be identified as target lesions at baseline. Target lesions should be selected on the basis of size (longest lesions) and suitability for accurate repeated measurements. Record the longest diameter for each lesion, except in the case of pathological lymph nodes for which the short axis should be recorded. The sum of the diameters (longest for non-nodal lesions, short axis for nodal lesions) for all target lesions at baseline will be the basis for comparison to assessments performed on study.

- If two target lesions coalesce the measurement of the coalesced mass is used. If a large target lesion splits, the sum of the parts is used.
- Measurements for target lesions that become small should continue to be recorded. If a target lesion becomes too small to measure, 0 mm should be recorded if the lesion is considered to have disappeared; otherwise a default value of 5 mm should be recorded.

NOTE: When nodal lesions decrease to <10 mm (normal), the actual measurement should still be recorded.

Non-target disease

All non-measurable disease is non-target. All measurable lesions not identified as target lesions are also included as non-target disease. Measurements are not required but rather assessments will be expressed as ABSENT, INDETERMINATE, PRESENT/NOT INCREASED, INCREASED. Multiple non-target lesions in one organ may be recorded as a single item on the case report form (eg, 'multiple enlarged pelvic lymph nodes' or 'multiple liver metastases').

OBJECTIVE RESPONSE STATUS AT EACH EVALUATION

Disease sites must be assessed using the same technique as baseline, including consistent administration of contrast and timing of scanning. If a change needs to be made the case must be discussed with the radiologist to determine if substitution is possible. If not, subsequent objective statuses are indeterminate.

Target disease

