- Complete Response (CR): Complete disappearance of all target lesions with the exception of nodal disease. All target nodes must decrease to normal size (short axis <10 mm). All target lesions must be assessed.
- Partial Response (PR): Greater than or equal to 30% decrease under baseline of the sum of diameters of all target measurable lesions. The short diameter is used in the sum for target nodes, while the longest diameter is used in the sum for all other target lesions. All target lesions must be assessed.
- Stable: Does not qualify for CR, PR or Progression. All target lesions must be assessed. Stable can follow PR only in the rare case that the sum increases by less than 20% from the nadir, but enough that a previously documented 30% decrease no longer holds.
- Objective Progression (PD): 20% increase in the sum of diameters of target measurable lesions above the smallest sum observed (over baseline if no decrease in the sum is observed during therapy), with a minimum absolute increase of 5 mm.
- Indeterminate. Progression has not been documented, and
 - one or more target measurable lesions have not been assessed;
 - or assessment methods used were inconsistent with those used at baseline;
 - or one or more target lesions cannot be measured accurately (eg, poorly visible unless due to being too small to measure);
 - or one or more target lesions were excised or irradiated and have not reappeared or increased.

Non-target disease

- CR: Disappearance of all non-target lesions and normalization of tumor marker levels. All lymph nodes must be 'normal' in size (<10 mm short axis).
- Non-CR/Non-PD: Persistence of any non-target lesions and/or tumor marker level above the normal limits.

- PD: Unequivocal progression of pre-existing lesions. Generally the overall tumor burden must increase sufficiently to merit discontinuation of therapy. In the presence of stable disease (SD) or PR in target disease, progression due to unequivocal increase in non-target disease should be rare.
- Indeterminate: Progression has not been determined and one or more non-target sites were not assessed or assessment methods were inconsistent with those used at baseline.

New Lesions

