The appearance of any new unequivocal malignant lesion indicates PD. If a new lesion is equivocal, for example due to its small size, continued assessment will clarify the etiology. If repeat assessments confirm the lesion, then progression should be recorded on the date of the initial assessment. A lesion identified in an area not previously scanned will be considered a new lesion.

Supplemental Investigations

- If CR determination depends on a residual lesion that decreased in size but did not disappear completely, it is recommended the residual lesion be investigated with biopsy or fine needle aspirate. If no disease is identified, objective status is CR.
- If progression determination depends on a lesion with an increase possibly due to necrosis, the lesion may be investigated with biopsy or fine needle aspirate to clarify status.

Subjective progression

Participants requiring discontinuation of treatment without objective evidence of disease progression should not be reported as PD on tumor assessment CRFs. This should be indicated on the end of treatment CRF as off treatment due to Global Deterioration of Health Status. Every effort should be made to document objective progression even after discontinuation of treatment.

Table 17. Objective Response Status at each Evaluation

Target Lesions	Non-target Disease	New Lesions	Objective status
CR	CR	No	CR
CR	Non-CR/Non-PD	No	PR
CR	Indeterminate or Missing	No	PR
PR	Non-CR/Non-PD, Indeterminate, or Missing	No	PR
SD	Non-CR/Non-PD, Indeterminate, or Missing	No	Stable
Indeterminate or Missing	Non-PD	No	Indeterminate
PD	Any	Yes or No	PD
Any	PD	Yes or No	PD
Any	Any	Yes	PD

Table 18. Objective Response Status at each Evaluation for Participants with Non-Target Disease Only

Non-target Disease	New Lesions	Objective status
CR	No	CR
Non-CR/Non-PD	No	Non-CR/Non-PD
Indeterminate	No	Indeterminate
Unequivocal progression	Yes or No	PD
Any	Yes	PD

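### Part 2 inclusion criterion 5 admits participants whose only measurable disease is in the axillary or inguinal nodes that Section 7.4 bars as target lesions; they can then count towards CBR only through CR

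*Protocol*

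**What the plan says.** Protocol Section 7.4 states that "the inguinal (limb) and axillary (arm) lymph nodes should not be used as target lesions". Its reason is that nodes draining the upper arm or thigh "may become enlarged following administration of the VBIR-2, and may not accurately reflect the status of underlying disease". The bar covers both basins, whichever limb is injected. The section makes no other exception: "Assessment of response will be made using RECIST version 1.1", with reference to Appendix 3.

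Part 2 inclusion criterion 5 (Section 4.1.2) reads in full "Measurable disease as per RECIST v. 1.1". It does not refer to Section 7.4.

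Appendix 3 counts a malignant node as measurable from 15 mm short axis on CT, at any site. It then says: "All measurable lesions not identified as target lesions are also included as non-target disease". For non-target disease, CR carries the condition "All lymph nodes must be 'normal' in size (<10 mm short axis"), and progression is defined as "PD: Unequivocal progression of pre-existing lesions". For new lesions, "The appearance of any new unequivocal malignant lesion indicates PD". None of these rules mentions vaccine-draining nodes. Appendix 3 of the SAP repeats them, also without an exception.

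Sections 2.2 and 9.4 define CBR, a Part 2 primary endpoint, as the proportion with CR, PR, or SD lasting more than 6 months. Section 9.3 plans about 30 Part 2 participants.

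**The concern.** Section 7.4 identifies a measurement problem and solves it for one of the places where these nodes enter the response assessment. Eligibility is left open: a node that may not serve as a target lesion can still be the lesion that makes someone eligible. The response table for participants without target lesions has no category for partial shrinkage or stability, so long disease control in such a participant is not counted in the primary efficacy endpoint.

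The nodes also remain in play as non-target lesions, as possible new lesions and in the CR condition. An expected local effect of the regimen could there be read as disease. At stake are a few points of CBR in a cohort of about 30, and the timing of some PFS events.

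**Working it through.** The plan states no figure on this point, so the check is a trace through the rules, followed by simple arithmetic.

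**1. Node-only participant**

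- Criterion 5 with the 15 mm rule in Appendix 3: a participant whose measurable lesions are all axillary or inguinal nodes is eligible.
- Section 7.4: none of those lesions may be a target lesion.
- Appendix 3: they become non-target disease, and Table 18 (non-target disease only) applies. Its statuses are CR, Non-CR/Non-PD, Indeterminate and PD.
- CBR counts CR, PR or SD > 6 months. Neither document maps Non-CR/Non-PD to SD.
- The only route into the CBR numerator is therefore CR, and that CR needs the same possibly reactive nodes to fall below 10 mm.
- ORR is affected in the same way, because PR is unavailable. PFS is not affected by this route, because Table 18 retains PD.

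**2. Size**

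Let k be the number of such participants among n = 30. The documents do not give k, so it is assumed. If none of them reaches CR, the highest attainable CBR is (30 − k)/30. If the true benefit rate is 30% in everyone and all of that benefit is PR or SD, the expected observed CBR is 0.30 × (30 − k)/30.

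| k (assumed) | Ceiling of CBR | Expected CBR at a true 30% |
|---|---|---|
| 0 | 100% | 30.0% |
| 1 | 96.7% | 29.0% |
| 2 | 93.3% | 28.0% |
| 3 | 90.0% | 27.0% |

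So 1/30 = 3.3 points is the most that one participant can cost. The loss is realised only if that participant would otherwise have had PR or SD > 6 months. As an illustration with the Jeffreys prior and the 20% reference rate used in Section 9.3, moving from 9/30 to 8/30 changes the posterior from Beta(9.5, 21.5) to Beta(8.5, 22.5), and P(rate > 20%) falls from 0.91 to 0.82. (The worked example in Section 9.3 itself does not reproduce: 14/30 gives 0.9995, not 77%. That is a separate matter.)

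**3. Reactive nodes when another measurable lesion exists (Table 17)**

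| How the swelling is read | CBR | ORR | PFS |
|---|---|---|---|
| Target CR with a recorded non-target node at 10 mm or more: scored PR | none | none | none |
| PD called after CR or PR was reached | none | none | event too early |
| PD called before any response and before 6 months of SD | lost, if benefit would have followed | lost, if response would have followed | event too early |

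The first row changes only the best-response category, because CBR and ORR both count PR. The second row leaves CBR and ORR intact because both ask whether a response was achieved; SAP Section 6.1 keeps any CR or PR in the ORR numerator, confirmed or not. It would shorten DOR.

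**4. Exposure and safeguards**

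Section 5.4 gives IM injections on both sides, in the deltoids or the vastus lateralis with the thigh preferred, at 4-week intervals during Cycles 1 and 2. A draining node may thus be stimulated again before a confirming scan 4 to 8 weeks later (Section 3.1.2). The SAP does not use that confirmation for PFS: Section 6.1 takes the first investigator PD under RECIST as the event. The SAP was written for the protocol of 16 March 2018, before Part 2 was specified.

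**The case against.** The strongest reply is that this is a rare edge case and that false progression is already well guarded.

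- **Rarity.** One measurable lesion anywhere else restores Table 17. The documents give no frequency of disease measurable only in axillary or inguinal nodes, and in NSCLC it is probably low. This stands, and it limits the size of the point. It does not reconcile criterion 5 with Section 7.4. CR also remains possible in Table 18. The wording of the bar would let a site choose such a node as target, but only against the intent of Section 7.4.
- **Safeguards.** Non-target progression must be unequivocal, should generally reflect a rise in overall tumour burden large enough to merit stopping therapy, and is described as rare when target disease is SD or PR. New lesions must be unequivocally malignant, and equivocal ones are followed further. Progression is to be confirmed at two timepoints. Section 7.4 itself warns assessors about these nodes. This largely stands: a reader might infer that the word unequivocal is the only protection, and that is not so. The residual gap is that confirmation tests persistence, not malignancy, and that the PFS event in the SAP does not wait for it.
- **Basins.** With thigh injections the axilla is not the basin draining the injected limb. This is correct for the secondary issue. It does not affect eligibility, because Section 7.4 bars both basins as target lesions whatever the injection site.

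**Conclusion.** The point holds for eligibility: criterion 5 and Section 7.4 do not fit together, and a node-only participant can enter the CBR numerator only through CR. Each such participant is 3.3 points of a denominator of 30. The number of such participants is unknown, may be zero, and is probably small. This part needs no assumption about how often nodes swell.

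The scoring issue is secondary. Reactive enlargement could be read as non-target or new-lesion PD, which brings a PFS event forward, and costs CBR only if it comes before any response and before 6 months of SD. The documents give no rate for it.

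Three stronger readings are not supported. A reader might infer that losing CR to a reactive node biases CBR, ORR and PFS; under Table 17 the result is PR, which counts in CBR and ORR and is not a PFS event. A reader might infer that every misclassified participant moves CBR by 3.3 points; most of the misclassifications above leave CBR unchanged. A reader might also take the 10 mm condition to catch any node that swells on treatment. Appendix 3 says that nodes under 10 mm are normal and are not followed as disease, so on its ordinary reading the condition concerns nodes already recorded as diseased.

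**What to change.** 1. In Section 4.1.2, criterion 5, require at least one RECIST 1.1 measurable lesion outside the axillary and inguinal nodes. This mirrors the existing bar in Section 7.4. The cost is that a rare node-only participant is not enrolled. Anyone enrolled before the change would still fall under Table 18 and should be identified when CBR is reported.
2. In Section 7.4 and Appendix 3, state that isolated enlargement of a node draining a used injection site is treated as equivocal under the continued-assessment rule that Appendix 3 already has for new lesions, and not as immediate PD. The wording must not stop isolated nodal progression from ever being scored. A rule that demanded pathology or progression elsewhere would do that, and in a single-arm study it would favour the regimen. The cost is that some true nodal progression is called only after further assessment.
3. Record the injection limb on the tumour assessment CRF, so that draining nodes can be identified.

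The total cost is wording in three places and one CRF field, with the matching text carried into Appendix 3 of the SAP.

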7.5. Tremelimumab and Sasanlimab Immunogenicity Assessments

In participants receiving tremelimumab, blood samples (approximately 5 mL, to provide at least 2 mL of serum) will be collected to detect anti-drug antibodies (ADA) and neutralizing antibody (NAb) against tremelimumab (~1 mL each of ADA and NAb). Similarly, in participants receiving sasanlimab, blood samples (approximately 5 mL, to provide at least 2 mL of serum) will be collected to detect ADA and NAb against sasanlimab (~1 mL each of ADA and NAb). The sampling schedule is specified in the [SOA](#).

Samples will be analyzed using a validated analytical method in compliance with Pfizer SOPs. The ADA sample analysis will follow a tiered approach of screening, confirmation, and titer determination. Only those samples tested positive for ADA will be further tested for NAb.

The immunogenicity samples must be processed and shipped as indicated in the instructions provided to the investigator site to maintain sample integrity. Any deviations from the immunogenicity sample handling procedure (eg, sample collection and processing steps, interim storage or shipping conditions), including any actions taken, must be documented and reported to the sponsor. On a case-by-case basis, the Sponsor may make a determination as to whether sample integrity has been compromised. Any deviation from the specified sample handling procedure resulting in compromised sample integrity will be considered a protocol deviation.

As part of understanding the immunogenicity of the investigational product, samples may be used for evaluation of the bioanalytical method. [CCI](#)

CCI

7.7. Other Assessments

7.7.1. Tumor and Medical History

History of the participant's disease under study including details of the primary diagnosis and treatment history will be collected within 28 before the start of treatment. In addition, a history of disease process other than the cancer under study (active or resolved) and concurrent illnesses will be collected. This will also include prior treatments and any current medical treatments for any condition.

8. ADVERSE EVENT REPORTING

8.1. Requirements

The [Table 14](#) below summarizes the requirements for recording safety events on the CRF and for reporting safety events on the Clinical Trial (CT) Serious Adverse Event (SAE) Report Form to Pfizer Safety. These requirements are delineated for 3 types of events: (1) SAEs; (2) non-serious adverse events (AEs); and (3) exposure to the investigational product under study during pregnancy or breastfeeding, and occupational exposure.

Table 14. Requirements for Recording Safety Events on the Case Report Form (CRF) and Reporting Safety Events on the Clinical Trial Serious Adverse Events Form

Safety Event	Recorded on the CRF	Reported on the CT SAE Report Form to Pfizer Safety Within 24 Hours of Awareness
SAE	All	All
Non-serious AE	All	None
Exposure to the investigational product under study during pregnancy or breastfeeding, and occupational exposure	All (regardless of whether associated with an AE), except occupational exposure	Exposure during pregnancy, exposure via breastfeeding, occupational exposure (regardless of whether associated with an AE)

All observed or volunteered events regardless of treatment group or suspected causal relationship to the investigational product(s) will be reported as described in the following paragraphs.

Events listed in the table above that require reporting to Pfizer Safety on the CT SAE Report Form within 24 hours of awareness of the event by the investigator **are to be reported regardless of whether the event is determined by the investigator to be related to an investigational product under study**. In particular, if the SAE is fatal or life-threatening, notification to Pfizer Safety must be made immediately, irrespective of the extent of available event information. This time frame also applies to additional new (follow-up) information on previously forwarded reports. In the rare situation that the investigator does not become immediately aware of the occurrence of an event, the investigator must report the event within 24 hours after learning of it and document the time of his/her first awareness of the event.

For each event, the investigator must pursue and obtain adequate information both to determine the outcome and to assess whether it meets the criteria for classification as an SAE (see the [Serious Adverse Events](#) section below). In addition, the investigator may be requested by Pfizer Safety to obtain specific follow-up information in an expedited fashion. This information is more detailed than that recorded on the CRF. In general, this will include a description of the event in sufficient detail to allow for a complete medical assessment of the case and independent determination of possible causality. Any information relevant to the event, such as concomitant medications and illnesses, must be provided. In the case of a participant death, a summary of available autopsy findings must be submitted as soon as possible to Pfizer Safety. Any pertinent additional information must be reported on the CT SAE Report Form; additional source documents (eg, medical records, CRF, laboratory data) are to be sent to Pfizer Safety **ONLY** upon request.

As part of ongoing safety reviews conducted by the sponsor, any non-serious AE that is determined by the sponsor to be serious will be reported by the sponsor as an SAE. To assist in the determination of case seriousness, further information may be requested from the investigator to provide clarity and understanding of the event in the context of the clinical study.

